4.1.2. Guidance for dose modification in case of adverse events

At any stage, the investigator can decide to permanently discontinue IMP for concerns regarding safety and tolerability, i.e. an AE including clinically significant abnormal laboratory tests. For abnormal liver function tests (LFTs), specific guidance is described in Appendix 9.

For the subsequent management of these AEs, the investigator can reduce the dose, interrupt, or permanently discontinue the IMP. Down-titration will be a one-step process to the lowest reduced dose. Once the AE has stabilized or improved, the dose can be increased again (re-escalation). For the re-escalation from the lowest reduced dose, an intermediate reduced dose level is required (Figure 2).

[figure not shown]

Figure 2: Study Drug Dose Modification: Down-titration and Re-escalation Steps

Tablet colors are for illustration purposes only

For all AEs, the investigator is advised to evaluate the concomitant medication, including local standard of care for the treatment of IPF, as part of the benefit-risk evaluation. The recommended duration of a different dose level or interruption for elevated LFTs is at least 2 weeks.

Elevated LFTs

At Visit 3 (randomization visit), blood samples are collected before IMP intake and the results of the laboratory tests will only be known after IMP intake. Therefore, if the LFTs are abnormal at this visit, the investigator needs to discontinue IMP (only if aspartate aminotransferase [AST] or alanine aminotransferase [ALT] $\geq 1.5x$ upper limit of normal [ULN], total bilirubin $\geq 1.5xULN$, and/or gamma glutamyl transferase [GGT] $\geq 3xULN$). It is recommended to consult the contract research organization (CRO) medical monitor (as per study contact list) or sponsor's study physician (if the former is not available).

At any visit from Visit 4 onwards:

Continue as planned: AST or ALT $\geq 1.5x$ to $3xULN$.

Discontinuation of IMP:

- AST or ALT >8xULN: permanently discontinue IMP with close observation*.
- AST or ALT \geq 3xULN with signs or symptoms of severe liver damage**: permanently discontinue IMP with close observation*.
- AST or ALT \geq 3xULN for more than 2 weeks
- AST or ALT \geq 3xULN during re-escalation (described below)

Down-titration to reduced dose level or interruption of IMP:

- AST or ALT \geq 3x to 5xULN without signs of severe liver damage**:

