At each visit, the subject will continue the intake of IMP (if confirmed by the responsible investigator or delegate, as detailed below) and will be supplied with IMP to cover the extended

visit windows (as described in Section 5.3). Urine pregnancy tests (if applicable) and subject diary cards may also be supplied to the subject's home.

Assessments and Activities to be performed at remote and on-site visits

For Visit 4 and all visits thereafter, if a randomized subject is not able to attend a scheduled study visit on site and a phone/televisit is conducted instead, then the study assessments should be conducted according to the Schedule of Activities (Section 6.11) as much as possible, in particular for Visits 9 and 12.

If possible and available, trained study staff or trained personnel are encouraged to carry out study assessments at the subject's home or another remote location (i.e. conduct phone call first, then conduct home/remote location visit).

Sites should assess risk to subjects' safety incurred by home (or other remote location) visits and ensure that the staff sent to the subject's home do not pose a risk of infection to the subject or vice versa.

At the phone/televisits or home (or other remote location) visits, the investigator should collect information on adverse events (changes of ongoing or new events), changes in concomitant medications or standard of care, and enquire about ongoing IMP intake (completion of subject diary cards).

At the home (or other remote location) visits, the following assessments should be performed (if appropriate as per Schedule of Activities, Section 6.11). If it is not possible to perform all assessments, every effort should be made to complete the assessments indicated with an asterisk (*).

- physical examination (including weight) *
- vital signs assessment *
- safety blood sample collection for central laboratory assessment where possible or local laboratory assessment (if sampling conditions as per laboratory manual cannot be ensured) *
- spirometry (using the study device) *
- 12-lead electrocardiogram (ECG) using the study device if possible or local assessment *
- electronic Clinical Outcome Assessment (eCOA) collection using the tablet device provided for the study *
- [REDACTED]
- urine pregnancy test (if applicable) *

In addition, all efforts should be made to review and collect the subject diary cards and perform drug accountability as well as retrieving the (un)used IMP blisters.

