The 6MWT and DLCO can be performed if circumstances allow.

Blood samples for PK, [REDACTED] should not be collected at home visits.

Additional guidance for on-site visits

If an on-site visit for randomized subjects is feasible, all assessments for the applicable visit should be performed according to the Schedule of Activities (Section 6.11). However, if it is not possible to conduct all the assessments, then the following assessments/activities should be prioritized:

- adverse events (changes of ongoing or new events) as well as information on hospitalization between visits
- changes in concomitant medications or standard of care, enquiring about ongoing IMP intake (completion of subject diary cards), as well accountability and return of (un)used IMP blisters
- vital signs
- safety blood sample collection (for central laboratory)
- spirometry and ECG (using the study devices)
- eCOA (using the tablet device provided for the study)
- 6MWT
- DLCO
- Urine pregnancy test (if applicable)

Guidance on continuation of IMP during the COVID-19 pandemic

The ultimate decision to continue or interrupt IMP remains with the investigator except when three consecutive on-site visits have been missed and could not be replaced by phone/televisits, home (or other remote location) visits, and/or local lab assessments, or if the safety assessments could not be performed within the indicated time periods. In these cases, IMP should be interrupted.

In general, the decision on IMP continuation shall depend on the investigator's assessment of the subject's clinical condition, and on the occurrence and severity of adverse events and the results of laboratory assessments.

Timely (in accordance to adjusted visit windows) local safety laboratory assessment and home/local ECG (if possible), are strongly recommended to support the decision regarding continuation of IMP. If these assessments are not feasible, then the investigator should collect minimal assessments, such as physical condition, adverse events, and concomitant medication to help decide on the subject's continuation of IMP. If only phone/televisits are possible, the decision to continue IMP may be based on this information.

The following criteria should be adhered to when making the decision on continuation of IMP and every effort should be made to capture safety assessments to ensure IMP can be continued. The recommendations are specific to the study phase:

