First phase: In case of missing visits between Visit 4 to Visit 8 (Week 2 to Week 18), safety assessments must be performed within an 8-week timeframe.

Second phase: In case of missing visits between Visit 9 to Visit 12 (Week 26 to Week 52), safety assessments must be performed within a 12-week timeframe.

Third phase: After Visit 12 (Week 52 to End of Study), safety assessments must be performed within a 16-week timeframe.

If during any of these phases, safety assessments at home or at another remote location are not feasible, then at a minimum, local laboratory evaluations are needed to evaluate if the subject can continue IMP. ECG alternatives are to be discussed with the medical monitor.

If IMP was interrupted, once safety assessments as specified above have been performed, the investigator may consider the re-start of IMP.

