Reference ranges will be supplied by the central laboratory. Clinical laboratory values outside the normal range will be flagged and clinical relevance will be assessed by the investigator. Clinically significant laboratory test abnormalities as judged by the investigator should be recorded as AEs. More frequent sampling as well as additional tests may be performed as deemed necessary by the investigator to follow up and resolve any safety concerns. In some circumstances, local laboratory results are allowed to be used (e.g. positive urine pregnancy test, abnormal liver function tests) for diagnosis of decision, but a central sample should also be collected and analyzed.

The details of sample collection, handling, storage, and shipment instructions will be provided in a separate laboratory manual.

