9.1.4. Adverse Events of Special Interest

Not applicable.

9.1.5. Clinical Laboratory Abnormalities and Other Abnormal Assessments as Adverse Events or Serious Adverse Events

Laboratory abnormalities without clinical significance based on the investigator's judgment, are not considered AEs or SAEs. However, laboratory abnormalities (e.g. clinical chemistry, hematology, and urinalysis) or other abnormal (clinical study-specific) assessments (e.g. ECG, radiography, vital signs) that require medical or surgical intervention, are associated with signs and/or symptoms, or lead to IMP interruption, modification, or discontinuation must be recorded as an AE or SAE if they meet the definition as described in Sections 9.1.1 and 9.1.2, respectively. If the laboratory abnormality is part of a syndrome, the syndrome or diagnosis is to be reported (e.g. anemia instead of decreased Hb).

The following liver enzyme elevations should be reported as SAEs:

- AST or ALT $\geq 8xULN$
- AST or ALT $\geq 3xULN$ with signs of severe liver damage (i.e. with the appearance of fatigue, nausea, vomiting, right upper quadrant pain or tenderness, fever, rash and/or eosinophilia [$>5\%$], and/or total bilirubin $\geq 1.5xULN$ or INR >1.5)

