#### Figure 1: Schematic Study Overview

D=Day, EoST/EoSA=end of study treatment/end of study assessments, FU=follow-up, V=Visit, W=Week.

Enrolled subjects will come to the clinical study center at screening (two visits from Day -28 to Day -1). Visit 2 of screening can only take place after confirmed IPF diagnosis on HRCT and LB (if applicable).

At Visit 3, eligible subjects will be randomized in a 1:1:1 ratio to receive GLPG1690 600 mg q.d., GLPG1690 200 mg q.d., or matching placebo for at least 52 weeks. Randomization will be stratified for background local standard of care for treatment of IPF.

Subjects will come to the clinical study center on Day 1 (baseline), Weeks 2, 4, 8, 12, 18, 26, 34, 42, 52, and every 12 weeks thereafter. Additional unscheduled visits are allowed if, in the investigator's opinion, further evaluation (clinical, laboratory, or other) is needed.

When the last subject reaches 52 weeks (Visit 12), subjects still taking IP and who had a scheduled visit at the clinical study center within 6 weeks before this date will be contacted by their investigator (phone call) to discontinue IP within 7 days after this date. Then the last scheduled visit will be documented as the end of study treatment (EoST) visit. These subjects will be invited to their follow-up visit scheduled at the clinical study center 4 weeks after their last dose of IP ( $\pm$ 7 days). For subjects still taking IP and who had their last scheduled visit more than 6 weeks before the date that the last subject reaches 52 weeks into the study (Visit 12), a scheduled visit will be planned within 2 weeks of this date for an EoST visit, followed by a follow-up visit 4 weeks later (visit at clinical center or phone call). Note that these subjects will continue IP intake until their EoST visit.

For subjects who, for any Coronavirus disease (COVID-19)-related reason, cannot perform study procedures, extended visit windows, the possibility to conduct phone/televisits and home (or other remote location) visits, and alternative assessment procedures are detailed in Section 6.1.1 of the CSP.

Subjects who discontinue IP early (early treatment discontinuation [ETD]), with the exception of patients lost to follow-up and patients who withdraw consent, will be encouraged to complete all following visits and evaluations as originally planned per protocol.

In particular, the subject will be requested if at all possible to attend:

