# 9.4.2. Laboratory Safety

Since all scheduled clinical laboratory evaluations will be performed by the central laboratory, only data from the central laboratory will be included, information from local labs will not be used. Lab tests that are not part of the planned test panels according to the protocol will only be listed.

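### SAP 9.4.2 discards all local-laboratory results on a premise that protocol Section 6.1.1 makes untrue for COVID-19-affected visits

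*SAP*

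**What the plan says.** SAP Section 9.4.2 rests on the premise that all scheduled laboratory evaluations are central, and concludes that "only data from the central laboratory will be included, information from local labs will not be used". Sections 9.4.2.7.1 and 9.4.2.7.2 repeat the exclusion for the worst-case abnormality and CTCAE grade derivations. SAP Section 2.4 names protocol version 7 as its basis, and SAP Section 2.3 notes that for COVID-19-affected subjects "alternative assessment procedures are detailed in Section 6.1.1 of the CSP".

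Protocol Section 6.1.1 provides for local testing in three places:

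- At home or remote visits it asks for "safety blood sample collection for central laboratory assessment where possible or local laboratory assessment", the local option applying when the laboratory manual's sampling conditions cannot be ensured.
- To support the decision on continuing IMP, timely "local safety laboratory assessment and home/local ECG (if possible), are strongly recommended".
- Where safety assessments at home or at a remote location are not feasible, "at a minimum, local laboratory evaluations are needed to evaluate if the subject can continue IMP".

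Protocol Section 6.6.2, the general rule, also permits local results in some circumstances, "but a central sample should also be collected and analyzed".

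**The concern.** The exclusion is justified by a statement that is false for a class of visits the protocol created on purpose. A subject can remain on IMP on the strength of a local result that the SAP then ignores. SAP version 2.0 added COVID-19 analyses, including tables of missed and virtual visits, but left this rule in place. It plans neither a listing of local results nor a count of visits with local results only, so a reader of the CSR could not judge the size of the gap.

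The affected outputs are ones the abbreviated CSR keeps: SAP Section 9.1 does not list 9.4.2 among the omitted analyses. They are the descriptive, shift, worst-case and CTCAE tables, and in 9.4.2.9 the Kaplan-Meier times to ALT/AST of at least 1.5, 3, 5 and 8xULN and the ALT/AST-with-bilirubin analyses. In the worst-case tables, a subject with other central results is scored on those alone. Under SAP Section 7.2, a subject with no central post-baseline result for a test leaves the denominator.

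**Working it through.** The plan gives no figure to reproduce. The check has three parts.

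**1. Does Section 6.1.1 remove the premise?** Section 6.6.2 asks for a parallel central sample. Section 6.6, however, sends COVID-19-affected visits to 6.1.1, and there local assessment is an alternative to central assessment, used because central sampling conditions cannot be met. Section 6.1.1 does not repeat the request for a central duplicate. On-site visits during the pandemic stay central under 6.1.1, so the gap concerns visits not held on site.

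**2. How late does a locally seen abnormality enter?** Inputs are the target days in SAP Table 2. (The protocol's schedule prints Day 237 for Week 34; the SAP's Day 239 = 34 x 7 + 1 is used.) Assume one local-only visit and no central retest. Delay = target day of the next scheduled visit minus target day of the local-only visit.

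| Local-only visit | Next central | Delay |
|---|---|---|
| Visit 4, Week 2 | Week 4 | 29 - 15 = 14 days (2 weeks) |
| Visit 5, Week 4 | Week 8 | 57 - 29 = 28 days (4 weeks) |
| Visit 6, Week 8 | Week 12 | 85 - 57 = 28 days (4 weeks) |
| Visit 7, Week 12 | Week 18 | 127 - 85 = 42 days (6 weeks) |
| Visit 8, Week 18 | Week 26 | 183 - 127 = 56 days (8 weeks) |
| Visit 9, Week 26 | Week 34 | 239 - 183 = 56 days (8 weeks) |
| Visit 10, Week 34 | Week 42 | 295 - 239 = 56 days (8 weeks) |
| Visit 11, Week 42 | Week 52 | 365 - 295 = 70 days (10 weeks) |
| Visit 12, Week 52 | Week 64 | 449 - 365 = 84 days (12 weeks) |
| Week 64 | Week 76 | 533 - 449 = 84 days (12 weeks) |

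All 9 scheduled post-baseline laboratory visits up to Week 52 (Visits 4 to 12), and the 12-weekly visits after, fall under 6.1.1. Two consecutive local-only visits give between 57 - 15 = 42 days and 533 - 365 = 168 days. An abnormality that resolves before the next central sample is lost altogether. The extended windows in 6.1.1 (up to 28 days either side at Visits 9 and 12) are not added.

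**3. What do other routes recover?** Protocol Section 9.1.5 says, among other triggers, that abnormalities that "lead to IMP interruption, modification, or discontinuation must be recorded as an AE or SAE" (if they meet the definitions), and makes AST/ALT of at least 8xULN, or at least 3xULN with signs of severe liver damage, reportable as SAEs. Section 6.6.2 adds clinically significant abnormalities as AEs. At 3xULN and above without signs of severe liver damage, up to 8xULN, Section 4.1.2 retests at 48 to 72 hours and at about 7 and 14 days, so any central retest cuts the delay to days.

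These routes are weakest at 1.5 to below 3xULN. From Visit 4, Section 4.1.2 says "Continue as planned: AST or ALT" in that band, so no IMP change forces an AE record and no retest is specified. Yet 1.5xULN is one of the four Kaplan-Meier thresholds in SAP 9.4.2.9. Nor do AE tables give the xULN level or the time to each threshold.

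**The case against.** Local replacement is a narrow fallback: central testing is preferred where possible, and pandemic-period on-site visits stay central. A subject whose Visit 4 is not expected to be on site should not be randomized, so the 2-week case should be exceptional. The measures date from May 2020 under a protocol first issued in 2018, so earlier visits are untouched. Nothing in 6.1.1 expressly revokes the parallel central sample, and unscheduled central samples are allowed and enter the worst-case tables. Central sampling is already 2 to 12 weeks apart, so onset is coarse for everyone. Access problems in a double-blind trial give no evident reason for imbalance between arms, and the laboratory analyses are descriptive. Serious elevations are captured as SAEs. Central-only summaries protect assay consistency, local reference ranges may not have been captured, and the programme has been cut to an abbreviated CSR.

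Much of this stands, and it limits the size. It means that 9 of 9 visits describes where the rule can apply, not how often it did, and that complete loss from a worst-case denominator should be rare. It supports keeping means and changes from baseline central-only. It does not rescue the premise, and it does not cover an asymptomatic elevation of 1.5 to below 3xULN seen only locally. Nor does it explain why results used to decide on continued IMP should be neither listed nor counted.

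**Conclusion.** The concern holds. As written, the rule removes safety data that the protocol itself relies on, for a reason that does not apply to the visits concerned. For each local-only visit without a central retest, entry into the laboratory analyses is nominally 2 to 12 weeks late, or the event is omitted if it has resolved.

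This assumes that no central sample was taken at that visit or soon after. How many subjects or visits meet that condition cannot be derived from the documents, so neither the effect on incidence nor any difference between arms can be stated; none is claimed. The laboratory displays are affected, most clearly at the 1.5xULN threshold. The serious liver cases should still appear in the AE and SAE tables. The rule should be corrected before the CSR tables are final; it does not bear on the primary efficacy analysis.

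**What to change.** 1. Correct the reason given in SAP 9.4.2: scheduled evaluations are central except where protocol Section 6.1.1 allowed local assessment.
2. List all local results.
3. Report by arm the number of subjects and visits with local-only results.
4. Add a version of the 9.4.2.7 and 9.4.2.9 analyses that includes local results obtained under 6.1.1, scaled to the local laboratory's own ULN or LLN where recorded and flagged by source, beside the central-only version.
5. Keep means and changes from baseline central-only.

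If local reference ranges were not captured, items 1 to 3 are the minimum. The documents do not show that they were, so item 4 may cover only part of the local results.

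The cost is a wording change, one listing, one count table, one extra run of existing tables and some mapping of local ranges. The downside is mixed assays in the added version, including local values set against central baselines; the source flag and the side-by-side display keep that visible. SAP Section 9.1 already allows changes after unblinding if they are explained in the CSR. No clinical rule changes.

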# 9.4.2.1. Laboratory Units

The statistical analysis will only present results in Conventional Units.

# 9.4.2.2. Derived Lab Tests

Estimated creatinine clearance, calculated according to Cockcroft-Gault calculation (Ccr):

 $C_{Cr}$  (in mL/min) = [(140-age) x weight]/[72 x  $S_{Cr}$ ] (x 0.85 for women), with  $S_{Cr}$  = serum creatinine in mg/dL, age in years and weight in kg

# 9.4.2.3. Handling Non-fasted Results

For laboratory tests like glucose, triglycerides and total serum bile acid that are sensitive to fasting, descriptive statistics and tabulations of Common Terminology Criteria for Adverse Events (CTCAE) toxicities (fasting only) will be shown by fasting status. Tabulations of scorings according to normal ranges will be created for both fasting and non-fasting results pooled. Laboratory results for which the fasting status is missing, will be considered as taken fasted

# 9.4.2.4. Scoring According to Normal Ranges

All values will be compared to their matching normal ranges. The normal ranges provided by the central laboratory will be used and are available in the database. Values will be scored as abnormally low (L), normal (N) or abnormally high (H): the variable LBNRIND in SDTM.LB dataset will be used in the analysis.

For glucose, triglycerides and total serum bile acid in non-fasting state the following limits are to be used:

Tests	Thresholds
Glucose (non-fasting)	>= 200 mg/dL
Triglycerides (non-fasting)	>= 200 mg/dL
Total serum bile acid (non-fasting)	>x 3 ULN1

Only for tests for which no toxicity gradings are specified in Section 9.4.2.5, analysis of the classification according to normal ranges will be done. Except for fasting sensitive tests like glucose and triglycerides. These will be summarized with scorings based on CTCAE/other

<sup>1 ULN: upper limit of normal range, LLN: lower limit of normal range

gradings for the fasted samples only, but also with scorings according to normal ranges for fasting and non-fasting samples pooled.

Any clinical significance flags related to these values will only be listed.

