#### 9.4.2.5. Scoring Based on CTCAE/Other Gradings

CTCAE version 5.0 classification is only for the tests listed below.

Tests	Thresholds (Conventional Unit		Thresho (SI Unit	Thresholds (SI Units)		
Hematology						
Hemoglobin (anemia) decreased	<lln-10< td="">g/dL	<lln-100< td="">g/L	G1	</lln-100<>	</lln-10<>	g/dL	<lln-100< td="">g/L	G1	</lln-100<>	g/L	G1	
	<10 - 8 <8	g/dL g/dL	<100 -80 <80	g/L g/L	G2 G3	
Hemoglobin increased (increase above ULN)	Increase >0-2	g/dL	Increase >0-20	g/L	G1	
	Increase >2-4 Increase>4	g/dL g/dL	Increase >20-40 Increase>40	g/L g/L	G2 G3	
White blood cell (WBC) count decreased	<lln-3000< td="">/mm3	<lln-3.0< td="">* 10^9/L	G1	</lln-3.0<>	</lln-3000<>	/mm3	<lln-3.0< td="">* 10^9/L	G1	</lln-3.0<>	* 10^9/L	G1	
	<3000 - 2000 < 2000-1000 <1000	/mm3 /mm3 /mm3	<3.0-2.0 < 2.0-1.0 <1.0	* 10^9/L * 10^9/L * 10^9/L	G2 G3 G4	
White blood cell (WBC) count increased	>100,000	/mm3	>100.0	* 10^9/L	G3	
Neutrophils decreased	< LLN-1500	/mm3	< LLN-1.5	* 10^9/L * 10^0/I	G1 G2	
	< 1000-500	/mm3	< 1.0-0.5	* 10^9/L * 10^9/L * 10^0/L	G2 G3	
Lymphocytes decreased	< 500	/mm3	< 0.5	* 10^9/L * 10^9/L	G4 G1	
	< 800-500 < 500-200	/mm3 /mm3	< 0.8-0.5 < 0.5-0.2	* 10^9/L * 10^9/L	G2 G3	
	< 200	/mm3	< 0.2	* 10^9/L	G4	
Lymphocytes increased	> 4000 > 20,000	/mm3 /mm3	> 4.0 > 20.0	* 10^9/L * 10^9/L	G2 G3	
Eosinophils absolute count	>ULN		>ULN		G1	
Eosinophils relative count	> 7%		> 7%		G1	
Platelets decreased	< LLN-75000	/mm3	< LLN-75.0	* 10^9/L	G1	

CONFIDENTIAL

Doc id 402993

	< 75000 – 50000	/mm3	< 75.0 - 50.0	* 10^9/L	G2
	< 50000-25000	/mm3	< 50.0-25.0	* 10^9/L	G3
	< 25000	/mm3	< 25.0	* 10^9/L	G 4
Coagulation					
Activated partial	> ULN - 1.5 x UL	N	> ULN - 1.5 x U	LN	Gl
thromboplastin time	> 1.5 - 2.5 x ULN	[	> 1.5 - 2.5 x ULN		G2
(aPTT)	> 2.5  x ULN		> 2.5  x ULN		G3
	> ULN - 1.5 x UL	N	> ULN - 1.5 x U	LN	
Prothrombin time (PT)	> 1.5 - 2.5 x ULN		> 1.5 - 2.5 x ULM	V	/
	> 2.5 x ULN		> 2.5 x ULN		
	1.2 – 1.5 xULN		> 1.2 - 1.5 xULN	1	G1
INR increased	> 1.5 - 2.5 xULN		> 1.5 - 2.5 xULN	ſ	G2
	> 2.5 xULN		> 2.5  xULN		G3
Chemistry					
Glucose decreased	< LLN – 55	mg/dL	< LLN - 3.0	mmol/L	G1
	< 55 - 40	mg/dL	< 3.0-2.2	mmol/L	G2
	< 40 - 30	mg/dL	< 2.2 -1.7	mmol/L	G3
	< 30	mg/dL	< 1.7	mmol/L	G4
Glucose increased (fasting)	> 130	mg/dL	> 7.2	mmol/L	/
	> ULN - 1.5 x UL	Ŋ	> ULN - 1.5 x U	G1	
Constitution in success 1	>1.5-3x ULN		>1.5-3x ULN		G2

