#### 9.4.2.7. Worst-Case Abnormality

#### 9.4.2.7.1. According to Normal Range

The worst-case postbaseline will be determined per subject, per laboratory test (and sense, if below and above) and for each analysis period. All non-missing postbaseline values (including unscheduled and follow-up visits, but excluding local laboratory results) will be used to derive the following worst-case:

- L = low: at least one post-baseline result is classified as L.
- N = normal: all post-baseline results are classified as N.

- H = high: at least one post-baseline result is classified as H.

If, for a subject, both L and H are reported, the subject will be counted twice in the table: once with a worst-case L and once with a worst-case H.

Tables will be created for treatment-emergent abnormalities, i.e. postbaseline abnormalities which differ from (and are not better than) the baseline result. If the baseline result is missing, a postbaseline abnormality L or H will always be considered as treatment-emergent.

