# 9.4.2.8. Analyses

No formal inferential statistics (p-values) will be derived.

For each laboratory test, descriptive statistics and graphical presentation (line plot of the mean and SE) will be provided for the actual laboratory values and change from baseline over time-by-treatment group.

A summary table per laboratory test category (hematology, biochemistry, urinalysis and coagulation), laboratory test and unit, treatment group and time point, showing only the mean value of actual values and changes from baseline will also be provided.

All laboratory abnormalities after the first dose of IP up to 30 days after the last dose will be included, consistently with AE reporting.

A shift table per laboratory test category (hematology, biochemistry, urinalysis and coagulation), laboratory test and treatment group will be provided for laboratory tests with normal ranges, for which CTCAE grades are not available. The table will present the worst shift in abnormality (L/N/...) during the treatment period versus the baseline abnormality (L/N/H).

Frequency table will be provided of the worst treatment-emergent laboratory abnormalities per laboratory test category (hematology, biochemistry, urinalysis and coagulation), laboratory test, and treatment group. This table will be created for those laboratory tests for which CTCAE grades are not available.

A shift table per laboratory test category (hematology, biochemistry and coagulation), laboratory test and treatment group for CTCAE grades will also be provided for selected tests only. The table will present the worst shift in CTCAE toxicity grade during the treatment period versus the baseline value.

A frequency table of the worst treatment-emergent laboratory CTCAE toxicity grades per laboratory test category (hematology, biochemistry and coagulation), laboratory test, and treatment group will be provided for selected tests only.

Shift table per laboratory test category (hematology, biochemistry, and urinalysis), laboratory test, and treatment group for laboratory tests with categorical data. The table will present the worst shift in value during the treatment period versus the baseline value.

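### The mandatory stop level for fasted total serum bile acid (>3xULN) has no category of its own in the SAP, so the number of subjects per arm reaching it cannot be read from the laboratory tables described

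*SAP*

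**What the plan says.** **Protocol.** Section 4.5.4 lists a fasted (at least 8 hours) total serum bile acid above 3xULN among the findings for which IMP will be discontinued. A random or postprandial value above 3xULN does not stop IMP. It leads to a fasted sample within 1 to 5 days, and that result decides. Exclusion criterion 29 (Section 4.5.2) removes subjects whose bile acid is above 3xULN. Section 6.6.2 does not require fasting for routine samples.

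**SAP.** Section 9.4.2.3 names bile acid with glucose and triglycerides as sensitive to fasting and says that "tabulations of Common Terminology Criteria for Adverse Events (CTCAE) toxicities (fasting only) will be shown by fasting status". It adds that "Tabulations of scorings according to normal ranges will be created for both fasting and non-fasting results pooled", and it treats a missing fasting status as fasted.

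Section 9.4.2.4 scores values low, normal or high. It then says: "For glucose, triglycerides and total serum bile acid in non-fasting state the following limits are to be used". For bile acid that limit is 3xULN. The same section states that only for "tests for which no toxicity gradings are specified in Section 9.4.2.5, analysis of the classification according to normal ranges will be done". Section 9.4.2.5 states that "CTCAE version 5.0 classification is only for the tests listed below". The list has a fasting row for glucose and one for triglycerides, but no row for bile acid. Section 9.4.2.9, on elevated liver function tests, covers AST, ALT and bilirubin only.

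Under 9.4.2.7.1 the worst case uses all post-baseline values, "including unscheduled and follow-up visits, but excluding local laboratory results". Treatment-emergent means "postbaseline abnormalities which differ from (and are not better than) the baseline result". Section 9.4.2.8 describes a shift table and a frequency table of treatment-emergent abnormalities for ungraded tests. Of the latter it says: "This table will be created for those laboratory tests for which CTCAE grades are not available".

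**The concern.** Bile acid is the protocol's cholestasis criterion, and crossing its fasted limit ends treatment. A safety reader will want to know how many subjects in each arm crossed it. Section 9.4.2.3 suggests that fasted bile acid will be tabulated by toxicity grade, but 9.4.2.5 supplies no grade, so that tabulation has nothing to work with. What remains is the low/normal/high scoring, and for a fasted sample its only upper cut is the ULN. A mild rise and a treatment-stopping rise then look alike. Some subjects who cross the stop level would also be missing from the treatment-emergent table.

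The laboratory tables are not among the analyses dropped in SAP 9.1, so the point still applies to the abbreviated CSR.

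**Working it through.** There is no sample size or alpha figure to reproduce. The check compares the protocol rule with the SAP scoring rules and traces example values through them. The values are illustrations, not data.

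**Step 1: cut-points.** Fasted or unknown status: high if >1xULN. Non-fasted: high if >3xULN. Protocol stop: fasted >3xULN.

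| Sample | SAP score | Meaning in the protocol |
|---|---|---|
| Fasted, 1.1xULN | High | No action |
| Fasted, 2.9xULN | High | No action |
| Fasted, 3.5xULN | High | Mandatory stop |
| Non-fasted, 2.9xULN | Not high | No action |
| Non-fasted, 3.5xULN | High | Fasted re-sample |
| Unknown status, 1.1xULN | High | No action |

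The pooled post-baseline high count mixes fasted or unknown >1xULN with non-fasted >3xULN. In the shift table, summed over baseline categories, it is at most an upper bound on subjects with a fasted value above 3xULN. Separating the two sample types would not yield the count, because the fasted part would still be cut only at 1xULN. The missing fasted 3xULN level is the cause, not the pooling. The result also does not depend on whether the database range indicator or the limits table in 9.4.2.4 takes precedence, since that table alters non-fasted samples only.

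**Step 2: treatment-emergent rule.**
- Fasted or unknown-status baseline 1.5xULN, later fasted 3.1xULN: 3.1 / 1.5 = 2.07-fold, past the stop level. Score: high to high. It does not differ from baseline, so it is not treatment-emergent. The same holds for any such baseline above ULN and up to 3xULN, and criterion 29 allows these.
- Non-fasted baseline 1.5xULN, later fasted 3.1xULN: the baseline is below the non-fasted limit. Score: not high to high, so it is treatment-emergent.

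**Step 3: normal fasted baseline.** One subject reaches 1.1xULN (1.1 / 3 = 37% of the stop level) and another 6xULN (6 / 3 = 200%). The values differ 6 / 1.1 = 5.5-fold. Both are scored normal to high and counted identically.

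**Step 4: other stop levels.** Four have a matching category by arm: AST/ALT >=8xULN and AST/ALT >=3xULN with bilirubin >=1.5xULN (SAP 9.4.2.9), and QTcF >500 ms and QTcF increase >60 ms (SAP 9.4.3.3). Others do not: AST/ALT >=3xULN for more than 2 weeks, AST/ALT >=3xULN during re-escalation, AST/ALT >=3xULN with symptoms or INR >1.5, and arrhythmia or conduction abnormality of Grade 3 or higher.

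**Step 5: other planned outputs.** Descriptive statistics by fasting status include a maximum (SAP 7.1, 9.4.2.3), which is not a count. They use the value nearest the target day in each window (SAP 6.3). A fasted retest could therefore be left out unless fasted and non-fasted values are windowed separately, which the SAP does not say.

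**The case against.** The strongest reply is that the SAP does not ignore 3xULN. Routine samples need not be fasted, and a routine value above 3xULN is what prompts the fasted retest. The SAP scores that value as high, so the detection step is covered. This stands. A reader might infer that the SAP has no 3xULN limit for bile acid at all, and the text contradicts that. What lacks a level is the confirmatory fasted result, which decides the stop.

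Second, the high-to-high case is narrower than it may look. Baseline is the last value before first dose (SAP 6.4) and need not be fasted. The case arises only when the baseline was fasted or its status is missing. Those subjects still appear in the shift table and drop out only of the treatment-emergent table. This also stands.

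Third, stopped subjects should be visible elsewhere. Laboratory abnormalities leading to discontinuation are recorded as AEs when they meet the AE definition (Protocol 9.1.5). TEAEs leading to IP discontinuation are tabulated by preferred term and arm (SAP 9.4.1.6.1), and so are reasons for discontinuation (SAP 9.2.2). It would be wrong to infer that the stops are hidden. But this route depends on the investigator acting and recording and on how the event is coded. It does not independently show how many subjects reached the level.

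Fourth, other stop rules also lack an exact category, so bile acid is not a singular omission. That is correct.

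Finally, the programme has ended, laboratory outputs carry no p-values, and mock tables sit in a separate document (SAP Section 1) not available here. These points limit the weight of the finding but do not supply the missing category.

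**Conclusion.** The point holds as a minor one. Under the SAP's stated rules, the number of subjects per arm with a fasted total serum bile acid above 3xULN cannot be read from the laboratory tables described. When the baseline is fasted or of unknown status and lies above ULN and up to 3xULN, crossing the stop level is not counted as treatment-emergent.

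The size cannot be put in arm percentages, because the documents give no event rates and no split of samples by fasting status. No bias in a treatment comparison is claimed. The conclusion assumes that the separate mock-table document does not already add a fasted 3xULN category.

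**What to change.** In SAP 9.4.2.9, add one table by treatment group:

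- **Rows:** worst post-baseline fasted bile acid in three levels (<=ULN, >ULN to 3xULN, >3xULN). Use all central laboratory values, including unscheduled retests, up to 30 days after last dose. Show post-baseline non-fasted values above 3xULN and unknown-status values in separate rows.
- **Columns:** baseline category, with separate columns for non-fasted baselines and for unknown or missing status, because these are not comparable with a fasted result.

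In the Step 2 example the fasted subject would then move from >ULN to 3xULN into >3xULN, and the two Step 3 subjects would fall in different cells. The pooled normal-range tables can stay. In 9.4.2.3, either refer to this table for bile acid or remove bile acid from the sentence on toxicity grades.

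The cost is one extra descriptive table from data already held. Locally analysed samples would remain uncounted, since SAP 9.4.2 uses central laboratory results only, so the AE and discontinuation tables are still needed alongside it.
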